## 9.4. Visit 6 (Week 40)

Visit 6 is to be conducted after 40 weeks ( $\pm 7$  days) of treatment in the extension study. At this visit, the patient (Track A only) will return all remaining study drug and the following assessments and procedures are to be completed in the following general order:

- Collect returned study medication from patient and perform drug accountability
- Assess study drug compliance
- Assess for occurrence of AEs
- Assess for changes in concomitant medications
- Obtain vital signs including weight
- Track A patients only: Draw blood for clinical laboratory tests
- For women of child-bearing potential, conduct urine pregnancy test
- Track A patients only: Inspect the oral cavity and document findings, if any
- Have the patient complete the PCL-S
- Have the patient complete the PROMIS-Sleep Disturbance Scale and SDS
- Have the patient complete the BDI-II
- Conduct the C-SSRS after reviewing the results of the BDI-II
- Conduct CGI-I comparing to the P306 baseline
- Track B patients only: Dispense 5 new bottles of TNX-102 SL tablets

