## 9.5. Visit 7 (Week 52)

Track B patients only: Visit 7 is to be conducted after 52 weeks ( $\pm 7$  days) of treatment in the extension study. At this visit, the patient will return all remaining study drug and the following assessments and procedures are to be completed in the following general order:

Collect returned study medication from patient and perform drug accountability

- Assess study drug compliance
- Assess for occurrence of AEs
- Assess for changes in concomitant medications
- Obtain vital signs including weight
- Draw blood for clinical laboratory tests
- For women of child-bearing potential, conduct urine pregnancy test
- Inspect the oral cavity and document findings, if any
- Have the patient complete the PCL-S
- Have the patient complete the PROMIS-Sleep Disturbance Scale and SDS
- Have the patient complete the BDI-II
- Conduct the C-SSRS after reviewing the results of the BDI-II
- Conduct CGI-I comparing to the P306 baseline

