# 12.1. Evaluation of Safety

Safety data will be summarized as a single treatment group receiving 1 or more doses of TNX-102 SL (patients that have taken only 1 tablet of TNX-102 SL will be included).

Safety will be assessed by the monitoring and recording of AEs, clinical laboratory tests, vital signs, visual examination of the oral cavity findings, the monitoring of suicidality using the Columbia C-SSRS scale, and patient-rated assessments of depressive symptomology (BDI-II) and PTSD symptomology (PCL-S).

AEs will be coded using the MedDRA and will be summarized overall and by preferred term and SOC. AEs will also be summarized by severity and relationship to study drug. SAEs and AEs leading to discontinuation of study drug will also be summarized.

Actual values and changes from the extension study baseline values for clinical laboratory test results and vital sign measurements will be summarized at endpoint using descriptive statistics (n, mean, standard deviation (SD), median, minimum, and maximum). Laboratory values will be displayed in the data listings along with corresponding normal ranges, and those that are outside the normal range will be flagged.

Based on the C-SSRS results, the frequency and severity of suicidal ideation and behavior will be tabulated at each time point. The number of patients with baseline and treatment-emergent suicidal ideation and/or suicidal behavior or self-injurious behavior, based on the C-SSRS, will be summarized by treatment group.

All data gathered will be listed by patient and parameter, and clinically significant abnormalities should be recorded as AEs. AEs of special interest indicating potential abuse and dependency will be evaluated and summarized as described in the Statistical Analysis Plan.

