6. ANALYSIS POPULATIONS

The following analysis populations are planned for this study:

• Safety Population (SAFETY): All participants who receive at least 1 dose of study drug in Study TNX-CY-P306. Participants who are issued study drug, but return 100% of it (i.e., none consumed) will be excluded from the Safety Population; likewise, participants that have no follow up following receipt of study drug to indicate they took drug are excluded. All analyses will be performed using this population, unless otherwise specified in this SAP.

Protocol: TNX-CY-P306 Page 14 of 36

Final v1.0

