7. GENERAL ISSUES FOR STATISTICAL ANALYSIS

7.1 General Statistical Methodology

Descriptive summaries will be provided where appropriate for each of the primary and secondary variables. In general, tables will summarize data by treatment group as defined in Section 3.2 and visit.

All tables will be completed for the Safety Population unless otherwise specified.

Continuous, quantitative, variable summaries will include the number of participants (N) with non-missing values, mean, standard deviation (SD), median, minimum, and maximum.

Categorical, qualitative, variable summaries will include the frequency and percentage of participants who are in the particular category. In general, the denominator for the percentage calculation will be based upon the total number of participants in the study population for the treatment group unless otherwise specified.

Unless otherwise noted, baseline values are defined as the last non-missing measurement prior to the first dose of open-label study drug in Study TNX-CY-P306. Change from baseline will be defined as the post-baseline visit value minus the baseline value.

ET participants will only be followed if required to monitor an on-going adverse event or other condition.

Participants are not supposed to change study sites; however, should this be necessary to allow a participant to continue in the study, participants will be analyzed under the site where they were initially enrolled.

Study day after first dose is defined as assessment date – first dose date +1. Dates prior to first dose are defined as assessment date – first dose date. Note that the protocol refers to "Day 0"; for the purposes of the datasets and analyses, this would appear as day 1.

All analyses will be performed using Statistical Analysis System (SAS®) Software version 9.4 or later.

Unless otherwise noted, 95% confidence intervals will be presented for statistical tests.

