10.2 Clinical Laboratory Evaluations

Laboratory data include analyses for Chemistry and Hematology and will be summarized by visit for the Safety Population. Descriptive summaries of actual values and change from baseline will be presented by study visit. 95% confidence intervals will be presented for change from baseline for each visit. ET data will be analyzed with the closest visit that does not have a valid assessment value.

Laboratory values will be displayed in the data listings and those that are outside the normal range ("H" or "L") will be flagged, along with corresponding normal ranges. Values pre-defined as potentially clinically significant ("HH" or "LL") will also be flagged. For each laboratory analysis, shifts in assessments of abnormality from baseline to each scheduled time point will be presented in shift tables.

A by-participant listing of all clinical laboratory data will also be provided.

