10.3 Columbia Suicide Severity Rating Scale (C-SSRS)

The C-SSRS is an instrument that measures suicidal ideation and behavior. Items measuring suicidal ideation and suicidal behavior are displayed in the table below. Frequency counts of yes/no responses to items below and whether any suicidal ideation or behavior is present will be summarized as described below.

The overall number of participants with any suicidal ideation or behavior (by type and in total) or self-injurious behavior while on-treatment will be provided by treatment group. For ideation, participants will only be counted once at each visit and/or time frame at the worst-case response for ideation type (1-5), where 1 is the least severe and 5 is the most severe type of ideation.

Category	Items
A) Suicidal	(1) Type 1: Wish to be dead
Ideation	(2) Type 2: Non-specific active suicidal thoughts
	(3) Type 3: Active suicidal ideation with any methods (not plan)
	without intent to act
	(4) Type 4: Active suicidal ideation with any some intent to act,
	without specific plan
	(5) Type 5: Active suicidal ideation with specific plan and intent
B) Suicidal	(1) Preparatory acts or behavior
Sehavior	(2) Aborted attempt
	(3) Interrupted attempt
	(4) Actual attempt
	(5) Completed suicide
	Suicidal Behavior present (composite of items 1-5)
	Non-Suicidal Self-Injurious Behavior

Suicidal intensity of ideation will be calculated by tallying up the five intensity items to create a total score ranging 0-25. If a participant does not have any suicidal ideation, a score of 0 will be given. Separate tables will be created for the entire Safety Population

Protocol: TNX-CY-P306 Page 23 of 36

Final v1.0

as well as the population comprising only participants exhibiting any suicidal ideation. Suicidal intensity of ideation total score will be summarized using descriptive statistics by treatment group.

A data listing of C-SSRS results will include only participants with suicidal ideation, suicidal behavior, or self-injurious behavior without suicidal intent. For participants with suicidal ideation, suicidal behavior, or self-injurious behavior without suicidal intent at any time, data from all visits are displayed.

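### By-visit laboratory-shift and C-SSRS percentages default to a denominator that includes patients not scheduled for assessment at that visit

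*SAP*

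**What the plan says.** **Default rule.** SAP 7.1 states: "Categorical, qualitative, variable summaries will include the frequency and percentage of participants who are in the particular category". It then sets the default: "the denominator for the percentage calculation will be based upon the total number of participants in the study population for the treatment group". The sentence is offered as a general rule and yields to any other specification.

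**Population.** The study population is the Safety Population of SAP 6: "All participants who receive at least 1 dose of study drug in Study TNX-CY-P306". Participants with no evidence of having taken drug are excluded, but no assessment at any particular visit is required.

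**Tables in question.** For laboratory tests, SAP 10.2 says "shifts in assessments of abnormality from baseline to each scheduled time point will be presented in shift tables". For the C-SSRS, SAP 10.3 counts each participant once per visit or time frame at the most severe ideation type, and Protocol 12.1 adds that "the frequency and severity of suicidal ideation and behavior will be tabulated at each time point". None of these places names a denominator.

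**Who is assessed.**
- Week 40 laboratory tests (Protocol 9.4): "Track A patients only: Draw blood for clinical laboratory tests".
- Week 52 (Protocol 9.5): "Track B patients only: Visit 7 is to be conducted after 52 weeks". Both laboratory tests and the C-SSRS are done there.
- Week 2 C-SSRS (Protocol 9.2 and Appendix 1): by telephone, only in patients entering directly from P301/HONOR.
- C-SSRS at Weeks 7, 16, 28 and 40: both tracks.

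**Where the SAP does address the question.** SAP 9.1.2 counts missing CGI-I as non-response. SAP 12.2 uses subjects with risk time in the interval for the long-term adverse event increments.

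**The concern.** A percentage in a by-visit safety table is normally read as the rate among patients who had the assessment. Under the default, the divisor also contains patients whom the schedule never sends for it. The error runs one way: the printed figure can equal the rate among those assessed or fall below it, and cannot exceed it. The shortfall is largest at the late visits, where whole tracks are absent by design, so a column of percentages can appear to decline over time simply because fewer patients are tested.

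The default also makes adjoining tables disagree. For continuous variables SAP 7.1 reports the number with non-missing values. At one visit, the mean of a laboratory parameter would rest on tested patients, while its shift percentages would rest on everyone in the group.

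**Working it through.** The plan gives no rate, sample size calculation, track split or retention figure for this point, so there is no stated figure to reproduce. The working is an identity plus labelled assumptions.

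**Identity.** Let p be the rate among assessed patients, n the number assessed at the visit and N the population.

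- Printed under the SAP default: p × n / N
- Printed with n as the divisor: p

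**Inputs.** N = 200, the enrolment ceiling in Protocol 6.2, used only for illustration. *Assumed:* p = 10%, Track A share f, and retention r (the same in both tracks).

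**Share assessed, before any early-termination (ET) results:**
- Week 28, laboratory and C-SSRS: r
- Week 40, laboratory: f × r
- Week 40, C-SSRS: r
- Week 52, laboratory and C-SSRS: (1 − f) × r

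**Base illustration, f = 50%, r = 100%.**
- Week 40 laboratory: n = 200 × 0.5 = 100, abnormal = 10, printed 10/200 = 5.0%.
- Week 52: n = 100, abnormal = 10, printed 5.0%.
- Week 40 C-SSRS: n = 200, printed 10.0%, so no dilution.

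In that Week 40 shift table the other 90 tested patients print as 90/200 = 45%. The cells total 50%, because the 100 untested patients fall in no cell.

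**Sensitivity, printed percentage where the true rate among tested is 10%:**

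| Track A share | Retention | Week 40 laboratory | Week 52 | Week 28, and Week 40 C-SSRS |
|---|---|---|---|---|
| 25% | 100% | 2.5 | 7.5 | 10.0 |
| 25% | 80% | 2.0 | 6.0 | 8.0 |
| 25% | 50% | 1.25 | 3.75 | 5.0 |
| 50% | 100% | 5.0 | 5.0 | 10.0 |
| 50% | 80% | 4.0 | 4.0 | 8.0 |
| 50% | 50% | 2.5 | 2.5 | 5.0 |
| 75% | 100% | 7.5 | 2.5 | 10.0 |
| 75% | 80% | 6.0 | 2.0 | 8.0 |
| 75% | 50% | 3.75 | 1.25 | 5.0 |

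**ET results.** Protocol 9.6 draws blood at the ET visit, and SAP 10.2 places the result at the closest visit lacking a valid value. A patient of either track who leaves after the Week 28 draw can therefore fill Week 40, so the rows with dropout are lower limits. At f = 50% and r = 80%, 40 patients have left. If none supplies a Week 40 value, the printed figure is 8/200 = 4.0%. If all 40 did, n = 80 + 40 = 120 and it is 12/200 = 6.0%. That outer limit needs every leaver to have Week 40 as the closest empty visit. Both figures stay below 10%.

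**Week 2 C-SSRS.** The printed figure is p times the share entering directly from P301, which the documents do not give.

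**The case against.** The strongest reply is that the plan does not mandate the bad percentage. The SAP 7.1 rule is hedged, and SAP 10.2 and 10.3 never mention percentages: one promises shift tables, the other frequency counts. A programmer might well use the number tested. This stands as mitigation only. SAP 7.1 attaches a percentage to categorical summaries in general, and using the number tested would depart from the only denominator the SAP states for these tables.

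A second reply is that n can be recovered from the yes/no counts, the shift cells or the adjoining laboratory summaries, which show non-missing n. SAP 15.1.2 also has the n shown with summary statistics be the non-missing n and has all planned categories displayed. This lessens the harm, but it leaves the percentage divisor unchanged.

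Several stronger readings are tempting and are not supported:

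- *Untested patients are classed as having no abnormality.* No rule in SAP 10.2 or 10.3 does this. They fall in no cell, and the normal or no percentages shrink as well. Where the SAP wants missing treated as an outcome, as for CGI-I, it says so.
- *C-SSRS loses a whole track at Week 40 as laboratory tests do.* It does not; Protocol 9.4 has it done in both tracks. From Week 7 to Week 40 only dropout matters. For Week 2, the visit windows in SAP 7.1.2 do not list that week, so it is unclear that such a table will appear.
- *Dropouts contribute nothing later.* ET laboratory results can, as shown in the working.
- *The prior-placebo column would print near zero at Week 40.* The protocol synopsis ties Track A to prior active drug, which points that way, but SAP 3 labels the tracks by source study. The effect on the group comparison cannot be settled from the documents.

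**Conclusion.** The point holds for the by-visit laboratory shift tables and the by-visit C-SSRS tables. The stated default is not overridden there, and it puts patients not scheduled for the assessment into the divisor. This is an unsuitable rule for these tables, and the gap arises from the visit schedule even if nobody drops out.

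The exact size depends on the track split and retention, which the documents do not give. At an assumed equal split with full retention, the printed figure is half the rate among tested patients for Week 40 laboratory tests and for Week 52. Dropout reduces it further, with ET results a partial offset.

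A reader might infer that the trial's long-term safety conclusions are diluted. The documents do not support that. SAP 12.4 classifies laboratory shifts by the highest or lowest post-baseline value, SAP 12.2 uses at-risk denominators for the adverse event increments, and for overall on-treatment C-SSRS counts the full Safety Population is a usual divisor. No test or decision rule depends on the by-visit percentages. Priority is moderate to minor.

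**What to change.** Add one sentence to SAP 7.1, or to both 10.2 and 10.3: for categorical summaries by visit, percentages are based on participants with a non-missing assessment at that visit and, for shifts, also a non-missing baseline. Print that n for each visit and treatment group. Keep the full Safety Population as the denominator for counts of any occurrence while on treatment.

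The cost is one SAP sentence and matching table-shell footnotes. No new data or visits are needed, and the change has no real downside.

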7.1.1 Adjustments for Multiplicity and Other Alpha Control

7.1.1.1 Multiplicity

No adjustments will be made from multiplicity and all p-values will be nominal.

7.1.2 Data Handling for Participants Who Discontinue Study Drug or Withdraw from the Study

Participants who withdraw/drop out from the study will have their ET visit data collected and included in the analysis based on the closest visit window (Week 7, 16, 28, 40, or 52). Visit windows will be assigned by splitting the periods between visits at the midpoint between the visits. If more than one record falls within the window, the one closest to the target date will be used in the analysis, with preference given to the scheduled visits in the case of equidistant visits.

Protocol: TNX-CY-P306 Page 15 of 36

Final v1.0

7.2 Efficacy Assessments

There is no formal testing order to the efficacy assessments in this protocol; however, they are described below in approximate order of importance.

7.2.1 Clinician Global Impression of Improvement (CGI-I)

The CGI-I will be completed by an Investigator to evaluate the participant's status since the start of the current study (P306). The CGI-I will be completed at each in-clinic visit after baseline. It will be the responsibility of the Principal Investigator or his qualified designee to assess change in the subject's overall status and answer the following question:

Since the initiation of treatment in P306, the participant is:

- 1 = Very much improved
- 2 = Much improved
- 3 = Minimally improved
- 4 =No change
- 5 = Minimally worse
- 6 = Much worse
- 7 =Very much worse

The primary analysis of CGI will treat it as a continuous variable (scored 1-7 as above). There will be an additional outcome presented where a responder on the CGI-I is defined a participant who is scored as 'Very much improved' or 'Much improved' and compared between the study arms.

7.2.2 Sheehan Disability Scale (SDS)

The SDS scale is a self-report questionnaire that was designed to assess the participant's view of the degree to which symptoms have disrupted work/school, social life/leisure activities, and family life/home responsibilities during the previous 2 weeks (Sheehan & Sheehan, 2008). In addition, the SDS asks the participant to provide the number of days of work/school lost as well as unproductive days in the past two weeks. The SDS scale will be completed by the participant at Baseline and after 7, 16, 27, and 40 weeks, plus 52 weeks for Track B participants. A total score will be calculated summing the three individual 11-point (0-10) scales. For participants that do not respond to the work/school disruption because the participant checked the box indicating he/she has not worked or attended school for reasons unrelated to the disorder (PTSD), the total score will sum the other 2 domain questions and multiply by 1.5 (rounding up to the nearest whole number) to maintain the scale of 0-30 for the total score. Participants with missing values on the other items will be missing for the total.

7.2.3 Other Efficacy Outcomes

7.2.3.1 PROMIS Sleep Disturbance Instrument

PROMIS refers to the Patient-Reported Outcome Measurement Information System (www.nihpromis.org), a National Institutes of Health (NIH)-funded initiative to develop instruments to be used across chronic conditions.

Protocol: TNX-CY-P306 Page 16 of 36

Final v1.0

The PROMIS sleep disturbance scale (short form 8a) will be assessed at Baseline and after 7, 16, 27, and 40 weeks, plus 52 weeks for Track B participants.

The sleep disturbance scale will be calculated summing the individual item scores of the 8 items. These summed scores will be transformed to T-scores using the published conversions (see Section 15.2).

7.2.3.2 BDI-II

The Beck Depression Inventory (BDI-II) is a 21-item measure of the severity of current depressive symptoms, extensively validated for use in both medical and mental health populations. While this instrument does not provide a psychiatric diagnosis of depression and has considerable overlap with PTSD associated symptoms, it does provide a continuous scale for measuring changes in the severity of symptomatology. The BDI-II will be completed by the participant at all in-clinic visits.

7.3 Safety Assessments

Safety will be assessed by:

- AE and SAEs throughout the entire duration of the study, including detailed assessment of AEs involving the oral cavity.
- Changes from baseline in clinical laboratory test results.
- Changes from baseline in vital signs and weight.
- Change from baseline in BDI-II (see Section 7.2.3).
- Suicidal ideation or behavior as assessed by the C-SSRS.

7.3.1 Adverse Event and Prior/Concomitant Medication handling conventions

To handle missing or partial prior/concomitant medication dates, the following rules will be applied.

For partial start dates:

- 1. If the year is unknown, then do not impute the date but assign a missing value.
- 2. If the month is unknown, then:
 - a. If the year matches the year of the first dose date, then impute the month and day of the first dose date.
 - b. Otherwise, assign "January."
- 3. If the day is unknown, then:
 - a. If the month and year match the month and year of the first dose date, then impute the day of the first dose date.
 - b. Otherwise, assign "01."

Protocol: TNX-CY-P306 Page 17 of 36

Final v1.0

For partial end dates:

1. If the year is unknown, then do not impute the date but assign a missing value.

- 2. If the month is unknown, then assign "December."
- 3. If the day is unknown, then assign the last day of the month.

After implementing the rules above, to determine whether medications with missing start or stop dates are prior or concomitant medications, the following strategy will be used:

- 1. If the start date and stop date are both missing, then the most conservative approach is taken and the medication is considered to be a concomitant medication.
- 2. If the start date is missing but the stop date is not missing and is after the day of first study dose administration, then the most conservative approach is taken and the medication is considered to be concomitant.
- 3. If the start date is missing but the stop date is not missing and is on or before the day of first study dose and after the date of signed informed consent, then the medication is considered to be a prior medication.
- 4. If the start date is not missing but the stop date is missing, then the most conservative approach is taken and medication is considered to be concomitant.

The missing severity of an AE will be imputed to "severe"; the missing relationship to study drug of an AE will be imputed to "possibly related".

